11.2.1. Important Medical Events (IME) & Pregnancy

Events that may not be immediately life-threatening or result in death or hospitalisation but may jeopardise the patient or may require intervention to prevent one of the other outcomes listed in the definition above should also be considered serious.

Although not a serious adverse event, any unplanned pregnancy will also be reported via

EudraCT Number: 2019-000171-16

Although not a serious adverse event, any unplanned pregnancy will also be reported via the SAE reporting system.

11.2.2. Reporting Responsibilities

King's College Hospital NHS Foundation Trust has delegated the delivery of the Sponsor's responsibility for Pharmacovigilance (as defined in Regulation 5 of the Medicines for Human Use (Clinical Trials) Regulations 2004 to the King's Health Partners Clinical Trials Office (KHP-CTO).

All SAEs, SARs and SUSARs will be reported immediately (and certainly no later than 24hrs) to the KHP-CTO and Chief Investigator in accordance with the current Pharmacovigilance Policy.

The KHP-CTO will report SUSARs to the regulatory authorities (MHRA). The Chief Investigator will report to the relevant ethics committee. Reporting timelines are as follows:

- SUSARs which are fatal or life-threatening must be reported not later than 7 days after the sponsor is first aware of the reaction. Any additional relevant information must be reported within a further 8 days.
- SUSARs that are not fatal or life-threatening must be reported within 15 days of the sponsor first becoming aware of the reaction.
- The Chief Investigator and KHP-CTO (on behalf of the sponsor), will submit a
 Development Safety Update Report (DSUR) relating to this trial IMP, to the MHRA
 and REC annually.

In cardiac surgery, post-operative transient complications are not unexpected and are not infrequent. The centres will only notify fatal and 'unexpected' non-fatal serious adverse events (SAEs) to the Trial Sponsor. Unexpected events are those not listed in the trial protocol or on the CRF. The sponsor will inform CTU if an event needs to be reported to the REC (usually only events that are both related to the intervention and unexpected). Centres will follow-up unexpected events to their conclusion or until the Trial Sponsor agrees that no further follow-up is necessary.

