6.3. Risks of the IMP and Comparator

An extremely rare side effect of volatile anaesthetic agents is malignant hyperthermia (MH), a genetic disorder with an incidence in the adult population of approximately 1:80,000- 1:200,000. The mortality of MH is less than 5% and treatment is dantrolene therapy. Diagnosis is via monitoring of temperature and end-expiratory CO2, both of which are common practice in cardiac anaesthesia. Patients with known malignant hyperthermia will not be included in this trial.

In addition, unspecific side effects of volatile anaesthetic agents include dose-dependent haemodynamic depression.

Unspecific side effects of propofol include bradycardia, tachycardia, hypotension, movement, burning/stinging/pain at the injection site, rash, and pruritus. In addition a prolonged infusion of propofol exceeding a dose of 4mg/kg/hr may very rarely result in rhabdomyolysis, metabolic acidosis, arrhythmias and cardiac failure.

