11.2. Procedures for recording and reporting adverse events

The Medicines for Human Use (Clinical Trials) Regulations 2004 and Amended Regulations 2006 gives the following definitions:

Adverse Event (AE): Any untoward medical occurrence in a subject to whom a medicinal product has been administered including occurrences which are not necessarily caused by or related to that product.

Adverse Reaction (AR): Any untoward and unintended response in a subject to an investigational medicinal product which is related to any dose administered to that subject.

Unexpected Adverse Reaction (UAR): An adverse reaction the nature and severity of which is not consistent with the information about the medicinal product in question set out in the summary of product characteristics (SmPC) for that product (for products with a marketing authorisation).

Serious Adverse Event (SAE), Serious Adverse Reaction (SAR) or Suspected Unexpected Serious Adverse Reaction (SUSAR): Any adverse event, adverse reaction or unexpected adverse reaction, respectively, that

- Results in death;
- Is life-threatening;
- Requires hospitalisation or prolongation of existing hospitalisation;
- Results in persistent or significant disability or incapacity;
- Consists of a congenital anomaly or birth defect.

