11.2.3. Adverse events that do not require reporting as an SAE

The following events are 'expected' following cardiac surgery and where they are relevant to the trial will be gathered in the CRF. There is no need for them to be reported as an AE or SAE:

- Cardiac arrest, requiring:
 - Resuscitation involving ventricular defibrillation/DC shock,
 - Chest reopening

- External/internal cardiac massage
- Haemodynamic support, including use of:
 - Any inotropes
 - Intra-aortic balloon pump (IABP)
 - Pulmonary artery catheter
 - Vasodilator
- Low cardiac output, requiring management with a Swan-Ganz catheter, IABP, or left ventricular assist device

- Arrhythmias, including:
 - Supraventricular tachycardia or atrial fibrillation requiring treatment
 - VF/VT requiring intervention
 - Pacing
- Pulmonary complications, including:
 - Re-intubation and ventilation
 - Tracheostomy
 - Initiation of mask CPAP ventilation after weaning from ventilation
 - ARDS
 - Pneumothorax or effusion requiring drainage
- Renal complications, including:
 - New haemofiltration/dialysis
 - Acute kidney injury
- Infective complications, including:
 - Wound infection
 - Respiratory infection
 - Sepsis (defined as antibiotic treatment for suspected infection, and the presence of systemic inflammatory response syndrome (SIRS) within 24 hours prior to start of antibiotic treatment)
- Thromboembolic complications, including:
 - Deep vein thrombosis
 - Pulmonary embolus
- Gl complications:
 - Peptic ulcer/GI bleed/perforation
 - Pancreatic (amylase > 1500iu)
 - Other (e.g. laparotomy, obstruction)
- Neurological complications:
 - Stroke
 - Transient ischaemic attack (TIA)
- Bleeding requiring reoperation
- Mediastinitis requiring reoperation
- Wound dehiscence requiring rewiring or treatment

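### Section 11.2.2 gives two SAE reporting rules that cannot both be followed, and the expectedness test and the 11.2.3 exemption leave some serious suspected drug reactions without a clear duty to report

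*Protocol*

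**What the plan says.** Four parts of the protocol bear on what a centre must report.

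- **General rule, section 11.2.2.** "All SAEs, SARs and SUSARs will be reported immediately (and certainly no later than 24hrs) to the KHP-CTO and Chief Investigator". The sentence has no exception and no cross-reference to 11.2.3.
- **Restricted rule, later in 11.2.2.** "The centres will only notify fatal and 'unexpected' non-fatal serious adverse events (SAEs) to the Trial Sponsor". The test follows at once: "Unexpected events are those not listed in the trial protocol or on the CRF".
- **Definition in section 11.2.** An adverse reaction is unexpected when its nature and severity are "not consistent with the information about the medicinal product in question set out in the summary of product characteristics (SmPC").
- **Exemption in section 11.2.3.** For a list of complications expected after cardiac surgery, "There is no need for them to be reported as an AE or SAE"; those relevant to the trial go on the CRF. The list includes cardiac arrest, arrhythmias, low cardiac output, acute kidney injury and stroke. It does not include myocardial infarction, malignant hyperthermia, rhabdomyolysis or metabolic acidosis.

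Section 6.3 describes the drug risks. For the volatile agents: "An extremely rare side effect of volatile anaesthetic agents is malignant hyperthermia (MH"). For prolonged high-dose propofol infusion it names rhabdomyolysis, metabolic acidosis, arrhythmias and cardiac failure.

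**The concern.** A centre cannot send every SAE and also send only some of them. The recipients differ in name, but the Sponsor "has delegated the delivery of the Sponsor's responsibility for Pharmacovigilance" to the KHP-CTO, so this does not separate the two duties.

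The test in the restricted rule is also loose. It asks whether an event is listed in the protocol or CRF, without confining this to 11.2.3 and without asking about severity or a suspected link to the anaesthetic. Section 11.2.3 does not ask about a suspected link either. A site could therefore follow one part of the text and hold back a serious suspected reaction to one of the two compared drugs.

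The 7-day and 15-day SUSAR deadlines in 11.2.2 run from the Sponsor's first awareness. An event that is never notified may not start that clock, and the annual safety report may miss it.

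**Working it through.** The protocol gives no figure for this point, so the main check applies each passage to the same serious events. The restricted rule is shown under two readings of 'listed': named anywhere in the protocol, or on the 11.2.3 list. The CRF is not available, so its effect is left open.

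| Serious event | General rule, 11.2.2 | Restricted rule, named anywhere | Restricted rule, 11.2.3 list | Exempt under 11.2.3? |
|---|---|---|---|---|
| Non-fatal malignant hyperthermia or rhabdomyolysis (named in 6.3, not on the list) | Report | Not notified | Notify, unless the CRF names it | No |
| Non-fatal cardiac arrest or arrhythmia attributed to the anaesthetic (on the list) | Report | Not notified | Not notified | Yes |
| Non-fatal myocardial infarction (endpoint in 5.7 and 5.8.4, not on the list) | Report | Not notified | Notify, unless the CRF names it | No |
| Fatal event of a listed kind, e.g. stroke | Report | Notify | Notify | Yes, as written |
| Non-fatal event named in neither protocol nor CRF | Report | Notify | Notify | No |

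Only the last row gives the same answer throughout. The second row does not depend on how 'listed' is read: the general rule requires a report, while the restricted rule and 11.2.3 do not. The fourth row sets 11.2.3 against both rules in 11.2.2.

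**Size for myocardial infarction.** Inputs: 22% (section 3.1) and 50 patients (section 9.1).

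0.22 × 50 = 11 expected cases

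This is an upper figure. It assumes that the cited rate applies to this population and to the 5.8.4 definition, and that every case is serious and non-fatal.

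**Size for malignant hyperthermia.** Inputs: incidence 1 in 80,000 to 1 in 200,000 (section 6.3), and 25 volatile-arm patients (50 allocated 1:1, section 9.1).

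25 / 80,000 = 0.0003; 25 / 200,000 = 0.0001 expected cases

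Malignant hyperthermia shows the gap in the wording. It is not an event this trial should expect to see.

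**The case against.** The best defence is that 11.2.2 states a general rule and then carves out routine surgical complications. The paragraph with the restricted rule opens by discussing transient postoperative complications. That rule speaks of SAEs and the exemption of AEs or SAEs, and neither names SARs or SUSARs. A serious reaction attributed to the anaesthetic is a SAR, so the general rule would still catch it. On this view 'listed' means the 11.2.3 list, and malignant hyperthermia is not on it. The two uses of 'unexpected' also differ in purpose: 11.2 classifies drug reactions, while 11.2.2 filters events in a surgical population.

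Much of this stands. A reader might infer that serious drug reactions would go unreported. The text does not support that, because the general rule still orders their reporting; the outcome is ambiguous. The malignant hyperthermia example also needs a mention in a risk description to count as listing.

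A reader might also add up the section 3.1 rates: 19 acute kidney injuries (0.38 × 50), 11 infarctions and 1 stroke (0.02 × 50), 31 in all. That total does not measure the problem. Twenty of the 31 are kidney injury or stroke, which 11.2.3 exempts deliberately. Kidney injury as defined in 5.8.6 need not be serious, and one patient may have several events.

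Other safeguards remain. The schedule in 8.1 collects MACCE and adverse events to 30 days, listed events relevant to the trial go on the CRF, and the DMC meets every six months (14.3).

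The defence does not remove the conflict. Under the 11.2 definitions a SAR is also an SAE, so limiting the restricted rule to SAEs does not clearly leave SARs out of it. The sentence on unexpected events refers to the whole protocol and the CRF. Nothing returns a listed event to the reporting route when it is attributed to the study drug.

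**Conclusion.** The point holds as a conflict in the safety-reporting text, and it should be fixed. The two rules in 11.2.2 are incompatible, and 11.2.3 conflicts with 11.2.2 on fatal listed events. For serious non-fatal suspected reactions the duty to notify is unclear. For those of a kind on the 11.2.3 list, such as cardiac arrest or arrhythmia, this is so on either reading of 'listed'. For those named only in 6.3 it depends on the literal reading.

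The largest practical effect is on myocardial infarction: up to about 11 of 50 patients, under the assumptions stated with that figure. The expected number of malignant hyperthermia cases is close to zero.

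The protocol rates the trial as Type A risk, and both techniques are standard care. No sample size, feasibility outcome or planned analysis changes. The CRF and the Pharmacovigilance Policy cited in 11.2.2 are not available; either could narrow the ambiguity in practice, but neither would remove the conflict from the protocol.

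**What to change.** Reconcile sections 11.2, 11.2.2 and 11.2.3 into one reporting rule.

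1. Keep the 24-hour rule as the general duty, and state the exemption as its only exception, with a cross-reference to 11.2.3.
2. Limit the exemption to non-fatal events on the 11.2.3 list that the investigator judges unrelated to the study anaesthetic.
3. For surgical events, define unexpected as not on the 11.2.3 list, in place of the present reference to the protocol or CRF. Keep the SmPC as the reference for suspected reactions only. It would not suit all events, since a product label does not settle whether wound dehiscence or mediastinitis is expected after surgery.
4. State whether myocardial infarction is on the 11.2.3 list.

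The cost is a change of wording and a few more SAE forms, for listed events that are fatal or judged related. If myocardial infarction stays off the list, its serious cases will also need forms, up to the number estimated above.

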11.2.3. Adverse events that do not require reporting as an SAE

The following events are 'expected' following cardiac surgery and where they are relevant to the trial will be gathered in the CRF. There is no need for them to be reported as an AE or SAE:

- Cardiac arrest, requiring:
 - Resuscitation involving ventricular defibrillation/DC shock,
 - Chest reopening

- External/internal cardiac massage
- Haemodynamic support, including use of:
 - Any inotropes
 - Intra-aortic balloon pump (IABP)
 - Pulmonary artery catheter
 - Vasodilator
- Low cardiac output, requiring management with a Swan-Ganz catheter, IABP, or left ventricular assist device

- Arrhythmias, including:
 - Supraventricular tachycardia or atrial fibrillation requiring treatment
 - VF/VT requiring intervention
 - Pacing
- Pulmonary complications, including:
 - Re-intubation and ventilation
 - Tracheostomy
 - Initiation of mask CPAP ventilation after weaning from ventilation
 - ARDS
 - Pneumothorax or effusion requiring drainage
- Renal complications, including:
 - New haemofiltration/dialysis
 - Acute kidney injury
- Infective complications, including:
 - Wound infection
 - Respiratory infection
 - Sepsis (defined as antibiotic treatment for suspected infection, and the presence of systemic inflammatory response syndrome (SIRS) within 24 hours prior to start of antibiotic treatment)
- Thromboembolic complications, including:
 - Deep vein thrombosis
 - Pulmonary embolus
- Gl complications:
 - Peptic ulcer/GI bleed/perforation
 - Pancreatic (amylase > 1500iu)
 - Other (e.g. laparotomy, obstruction)
- Neurological complications:
 - Stroke
 - Transient ischaemic attack (TIA)
- Bleeding requiring reoperation
- Mediastinitis requiring reoperation
- Wound dehiscence requiring rewiring or treatment

11.3. Treatment stopping rules

The trial may be prematurely discontinued by the Sponsor, Chief Investigator or Regulatory Authority on the basis of new safety information or for other reasons given by the DMC, regulatory authority or ethics committee concerned.

EudraCT Number: 2019-000171-16

If the trial is prematurely discontinued, active participants will be informed and no further participant data will be collected. The Competent Authority and Research Ethics Committee will be informed within 15 days of the early termination of the trial.

12. Blinding and unblinding

Staff at each site, and at the LSHTM CTU, will be arranged into blinded and unblinded teams. This will be recorded in the delegation log at each organisation.

For the duration of the trial, staff may move from the blinded team to the unblinded team, but not from the unblinded team to the blinded team.

The unblinded teams will look after the patient in theatres, and include the anaesthetist and the research nurse collecting intraoperative data. The blinded teams include medical teams looking after the patient from arrival at the postoperative cardiac recovery onwards and research nurse teams collecting postoperative follow-up data.

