5.7. Secondary objectives

- Feasibility of collecting event data in more than 95% of enrolled patients at the 30 day follow-up.
- Assessment of effectiveness of patient identification and screening processes.
- Identification and analysis of any reasons for failure to recruit patients.
- Assessment of trial processes, including the choice of outcome measures and impact on staff.
- Assessment on the feasibility of collecting the following, planned to be endpoints in the full trial:
 - Low Cardiac Output Syndrome
 - Myocardial injury, assessed by ischaemic serum markers: hsTnT, MyC, preoperatively, at 6 hrs after arrival in CCU and on the 1st and 2nd postoperative mornings, area under the curve and peak postoperative levels
 - MACCE (stroke, non-fatal myocardial infarction, death from any cause) at 30 days
 - Cardiac related mortality at 30 days
 - Postoperative in hospital atrial fibrillation requiring treatment
 - Acute kidney injury (according to KDIGO)
 - In-hospital postoperative delirium (assessed by the confusion assessment method) [17]
 - Respiratory complications needing prolonged ventilation (>24 hours)
 - Length of stay in the critical care unit (CCU)
 - Length of hospital stay
 - WHO Disability Assessment Schedule (WHODAS) at 30 days [18]
 - Quality of Life Questionnaire, Eurogol EQ-5D-5L at baseline and 30 days
 - Days alive and at home until 30 days after surgery

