10.2. Withdrawal of patients

Participants have the right to withdraw from the study at any time for any reason. The investigator also has the right to withdraw patients from the study drug in the event of inter-current illness, AEs, SAEs, SUSARs, protocol violations, cure, administrative reasons or other reasons. It is understood by all concerned that an excessive rate of withdrawals

can render the study un-interpretable; therefore, unnecessary withdrawal of patients should be avoided. Should a patient decide to withdraw from the study, all efforts will be made to report the reason for withdrawal as thoroughly as possible. Should a patient withdraw from study drug only, efforts will be made to continue to obtain follow-up data, with the permission of the patient. A patient may decide to withdraw from the trial at any time without prejudice to their future care.

EudraCT Number: 2019-000171-16

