10.2.3. Follow up of patients withdrawing from the trial

Patients who withdraw from the trial will undergo standard clinical care. Patients will be encouraged to allow data and samples that have been collected before withdrawal to be used in the analyses. If consent to use data is also withdrawn, then these will be discarded. Appropriate handover of patients withdrawing from the trial will occur so their local clinical team can arrange their ongoing treatment.

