11.1. Specification, timing and recording of safety parameters

Patients will undergo a pre-operative assessment by trained healthcare professionals. All safety requirements in place for CABG surgery will be applied in this study. Any patient deemed unfit or unsafe to participate, or meets any exclusion criteria, will not be included in the study.

Safety reporting for each patient should commence from time of randomisation to completion of follow up at 30 days after randomisation.

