13.1. Data handling and record keeping

Data will be kept for 15 years following completion of the trial. The data controller for the trial is King's College Hospital (Sponsor) and the data processor is LSHTM. They are both based in the United Kingdom.

Patient data will be kept confidential and managed in accordance with the General Data Protection Regulations 2018, NHS Caldecott principles, The Research Governance

Framework for Health and Social Care, and the conditions of Research Ethics Committee Approval.

EudraCT Number: 2019-000171-16

Patients' rights to access, change or move their information are limited, as we need to manage information in specific ways in order for the research to be reliable and accurate. If patients withdraw from the study, we will keep the information that we have already obtained and we will use the minimum personally-identifiable information possible. Further information about this can be found here:

https://www.kch.nhs.uk/about/corporate/ data-protection

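### Protocol 11.3 ends all data collection if the trial stops early, which contradicts the 30-day safety reporting in 11.1 and the event follow-up in 11.2.2

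*Protocol*

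**What the plan says.** Section 11.3 is headed as treatment stopping rules, but its text concerns discontinuation of the whole trial. The sponsor, the chief investigator or the regulator may stop it "on the basis of new safety information or for other reasons given by the DMC, regulatory authority or ethics committee concerned". The consequence follows: "If the trial is prematurely discontinued, active participants will be informed and no further participant data will be collected". No exception is made for patients who have already been randomised and treated.

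Two other safety sections point the other way:

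- Section 11.1: "Safety reporting for each patient should commence from time of randomisation to completion of follow up at 30 days after randomisation".
- Section 11.2.2: "Centres will follow-up unexpected events to their conclusion or until the Trial Sponsor agrees that no further follow-up is necessary".

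On withdrawal, section 10.2 aims to keep follow-up going when only the study drug is stopped: "Should a patient withdraw from study drug only, efforts will be made to continue to obtain follow-up data, with the permission of the patient". For patients who leave the trial, section 10.2.3 says of data and samples already collected: "If consent to use data is also withdrawn, then these will be discarded". The section on data handling and record keeping (the second of two numbered 13.1) says: "If patients withdraw from the study, we will keep the information that we have already obtained". It attaches no condition.

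**The concern.** A rule that ends data collection with the trial might do little harm if treatment were continuing and the stop ended it. Here the randomised treatment is over by the end of surgery (section 6.2), and the outcome period is what follows. A stop cannot reduce the exposure of a patient who has already had the operation. Under 11.3 its only effect on that patient is that the trial no longer records what happens next.

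The timing makes this worse. New safety information is a named ground for stopping, so the rule applies when events in the most recently treated patients are of most interest to the sponsor, the DMC and the regulator. A site would also hold conflicting instructions: 11.3 tells it to collect nothing more, while 11.1 and 11.2.2 tell it to carry on.

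The withdrawal wording raises a separate and narrower problem. For a patient who also withdraws consent to the use of data, one section says discard and the other says keep.

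**Working it through.** The protocol gives no figure to reproduce on this point. The check sets the text side by side and then estimates how many patients the rule would reach.

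**Step 1: does stopping spare exposure?** Randomisation is on the morning of surgery (7.2). The volatile agent runs from induction to the end of surgery, and propofol as the randomised agent is confined to the procedure (6.2). MACCE, adverse events, days at home, EQ-5D-5L and WHODAS are collected at 30 days after randomisation (8.2.7). So for nearly all of the 30 days there is no randomised treatment left to stop.

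**Step 2: compare the rules after an early stop.**

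| Section | Instruction | Exception for an early stop? |
|---|---|---|
| 11.3 | Collect no further participant data | None for patients already treated |
| 11.1 | Safety reporting for each patient to day 30 | None stated |
| 11.2.2 | Follow unexpected events to conclusion, or until the sponsor agrees to end | None stated |

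The first row cannot be followed together with the other two. It also departs from the protocol's approach elsewhere: 10.2, 10.2.2 and 10.2.5 each try to preserve event data, after study drug withdrawal, opt-out from active follow-up and loss of capacity respectively.

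**Step 3: would SAE reporting fill the gap?** Only in part. Under 11.2.2 centres notify fatal events and unexpected non-fatal SAEs. Section 11.2.3 lists stroke, low cardiac output, acute kidney injury, cardiac arrest and arrhythmias, among others, as expected. These are exempt from AE and SAE reporting and are gathered in the CRF where relevant. If CRF collection ends, non-fatal events of these types have no stated route to the sponsor. Several are planned endpoints of the main trial (5.7).

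**Step 4: how many patients?**

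- Inputs: 50 patients in about 10 months (5.6); safety period of 30 days from randomisation (11.1).
- Assumption: even accrual.
- Accrual rate: 50 / 10 = 5 per month.
- Days per month: 365.25 / 12 = 30.44.
- Patients inside their 30 days at a stop: 5 × 30 / 30.44 = 4.9, or about 5.
- Share of those enrolled: 4.9 / 25 = 20% for a stop at month 5; 4.9 / 50 = 10% for a stop as recruitment ends.
- Average follow-up still to come for these patients: 30 / 2 = 15 days.
- Of the 4.9, those in the first three days, when the biomarker and LCOS data are still being collected: 5 × 3 / 30.44 = 0.5.

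So most of the affected patients would already have their early postoperative data and would lose the later part of follow-up, including the 30-day contact.

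**Step 5: withdrawal.** For ordinary withdrawal, 10.2.3 and 13.1 agree: data already obtained are retained. They part only when consent to use the data is also withdrawn. Then 10.2.3 discards and 13.1, which has no exception, keeps.

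**The case against.** The strongest reply is that this matters only if the trial stops early. That is unlikely for a 50-patient feasibility trial of two standard techniques, classed as no higher in risk than standard care (section 4). If the trial runs to plan, nothing is lost. Outcome analyses are exploratory and effect sizes are not to be interpreted (9.3). Sections 11.1 and 11.2.2 could also be taken to keep safety reporting alive whatever 11.3 says. The points on likelihood and on the exploratory analyses stand, and they keep the severity moderate. The last point does not remove the problem: it is the contradiction itself, and step 3 shows that notification alone would miss expected non-fatal events. Section 11.2.2 does open with a broader sentence on reporting all SAEs, but the later text there and in 11.2.3 narrows it.

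Several stronger readings are tempting, and the protocol does not support them:

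- **Recently treated patients would never be observed.** Section 11.3 stops further collection and deletes nothing; only the remainder is lost.
- **The intention-to-treat set would be truncated.** Missing later outcomes leave the set of randomised patients unchanged.
- **About 7 patients are affected.** That figure comes from adding the 14 days allowed for a late telephone contact (8.2.7). Safety reporting ends at day 30, so about 5 is the relevant count.
- **A stop would breach the 95% follow-up target.** The target, "Feasibility of collecting event data in more than 95% of enrolled patients at the 30 day follow-up", is a feasibility aim for the planned trial. It is not a limit for a trial halted on safety grounds.
- **Discarding withdrawn patients' data would flatter the follow-up rate.** The target already refers to enrolled patients, 10.2.1 makes the withdrawal rate a key secondary outcome, and 10.2.2 offers collection of events from the notes. Nothing says that withdrawn patients leave the denominator.

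**Conclusion.** The point holds as an internal contradiction joined to a poorly chosen rule. Section 11.3 cannot be followed together with 11.1 and 11.2.2. Followed as written, it would end observation of patients already exposed, with no gain in their protection, and would leave expected non-fatal complications without a stated reporting route.

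About 5 patients would be affected at a stop, each losing the rest of a 30-day follow-up, on average about 15 days. Both figures rest on even accrual at the planned 5 per month. Slower recruitment would lower the count in proportion, and clustered recruitment could move it either way.

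Severity is moderate: the rule bites only on an early stop, but that is the situation it was written for. The conflict between 10.2.3 and 13.1 is real but minor and is confined to patients who also withdraw consent to data use. Neither matter can be left to an analysis plan, because both are instructions to sites and the sponsor on collecting and keeping data.

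**What to change.** Amend 11.3 so that, on premature discontinuation, no further participants are randomised, while follow-up, safety reporting and data entry continue to day 30 for all participants already randomised unless they withdraw consent. Refer to 11.1 and 11.2.2 so that the three sections agree.

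Separately, write one rule for data collected before withdrawal and use it in both 10.2.3 and 13.1, stating what happens when consent to use the data is also withdrawn.

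The cost is protocol wording plus, after a stop, the remaining scheduled contacts for about 5 patients. These visits and calls are already in section 8.2. The protocol does not say whether funding would continue after an early stop, so the sponsor should confirm that this short close-out is covered.
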